
Other Secondary^b
 
To assess whether mirikizumab induction dosing is superior to placebo with respect to an early, clinically meaningful response
 
To compare mirikizumab to placebo with respect to clinical response and time to clinical response during the induction dosing period, and with respect to patient-reported outcomes during the induction dosing period
	
At Week 4:
 
 • Proportion of patients achieving PASI 75 
At Week 16 and various time points over the first 16 weeks of dosing:
 
 • Proportion of patients achieving PASI 90 • Change from baseline in PPASI total score in patients with palmoplantar involvement at baseline • Change in PSSI total score in patients with scalp involvement at baseline • Change from baseline in NAPSI total score in patients with fingernail involvement at baseline • Change from baseline on the SF-36 physical component summary (PCS) and mental component summary (MCS) • Change from baseline on PatGA of disease severity** • Change from baseline for the WPAI PSO scores (Absenteeism, Presenteeism, Work Productivity Loss, and Activity Impairment) • Change from baseline in QIDS-SR16 total score in those with a baseline QIDS-SR16 total score ≥ 11 • Proportion of patients achieving a DLQI total score of (0,1) with at least a 5-point improvement (reduction) from baseline in patients with a baseline DLQI total score ≥ 5 • Proportion of patients achieving DLQI (0,1) with DLQI baseline score > 1

Protocol-Defined Objectives and Endpoints

Objectives	Endpoints

To compare mirikizumab to secukinumab with respect to clinical response and time to clinical response during the induction dosing period, and with respect to patient-reported outcomes during the induction dosing period
 
To assess whether 250-mg mirikizumab Q8W and 125-mg mirikizumab Q8W maintenance dosing is noninferior to secukinumab with respect to high levels of clinical response
	
At Week 16 and various time points over the first 16 weeks of dosing:
 
 • Proportion of patients achieving PASI 90 
At Week 24:
 
 • Proportion of patients achieving PASI 90 
At Week 52:
 
 • Proportion of patients achieving an sPGA (0)

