		DLQI daily activities domain	Sum of responses of questions #3 and #4: #3. How much has your skin interfered with you going shopping or looking after your home or garden? #4. How much has your skin influenced the clothes you wear?	If 1 question in a domain is missing, that domain is missing.
		DLQI leisure domain	Sum of responses of questions #5 and #6: #5. How much has your skin affected any social or leisure activities? #6. How much has your skin make it difficult for you to do any sport?	If 1 question in a domain is missing, that domain is missing.
		DLQI work and school domain	Sum of responses of questions question #7A and #7B: #7A. Has your skin prevented you from working or studying? #7B. If No: how much has your skin been a problem at work or studying?	If the answer to question #7A is missing, this domain is missing. If #7A is No, and #7B is missing, this domain is missing.
		DLQI personal relationships domain	Sum of responses of questions #8 and #9: #8. How much has your skin created problems with your partner or any of your close friends or relatives? #9. How much has your skin caused any sexual difficulties?	If 1 question in a domain is missing, that domain is missing.
		DLQI treatment domain	Response of question #10: #10. How much of a problem has the treatment for your skin been, for example by making your home messy, or by taking up time?	If 1 question in a domain is missing, that domain is missing.
WPAI-PSO	The Work Productivity and Activity Impairment-Psoriasis (WPAI-PSO) Questionnaire is a patient-reported instrument developed to measure the	Employment Status	Yes/No	Missing if question is missing
		Absenteeism Score (%)	$\frac{Q2}{(Q2 + Q4)} \times 100$	Missing if Q2 or Q4 are missing. Also missing if

Measure	Description	Variable	Derivation/Comment	Imputation Approach if with Missing Components
	impact on work productivity and regular activities attributable to a specific health problem (psoriasis). It contains 6 items that measure: 1) employment for pay status, 2) hours missed from work due to the psoriasis, 3) hours missed from work for other reasons, 4) hours actually worked, 5) degree of health-affected productivity while working, and 6) degree of health affected productivity in regular unpaid activities. Greater scores indicate greater impairment (Reilly Associates Health Outcomes Research [WWW]).			Employment Status is No.

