		Presenteeism Score (%)	$\frac{Q5}{10} \times 100$	Missing if Q5 is missing. Also missing if Employment Status is No.
		Work Productivity Loss Score (%)	$\left[\frac{Q2}{Q2 + Q4} + \left(1 - \frac{Q2}{Q2 + Q4} \right) \frac{Q5}{10} \right] \times 100$	Missing if Q2, Q4, or Q5 is missing. Also missing if Employment Status is No.
		Activity Impairment Score (%)	$\frac{Q6}{10} \times 100$	Missing if Q6 is missing. May still be present and nonmissing if patient is unemployed.
SF-36	The SF-36 Version 2 is a 36-item, patient-completed measure designed to be a short, multipurpose assessment of health (The SF Community – SF-36 Health Survey Update). The summary scores range from 0-100, with higher scores indicating better levels of function and/or better health. Items are answered on Likert scales of varying lengths. The SF-36 comprises 8 domain scores and 2 overarching component scores. SF-36 domain scores are: (1) Physical functioning, (2) Role-physical, (3) Role-emotional, (4) bodily pain, (5) vitality, (6) social functioning, (7) mental health, and (8) general health. The component scores are: (1) the Physical Component Summary (PCS) and (2) Mental Component Summary (MCS).	SF-36 Domain scores and SF-36 Component Scores	Per copyright owner, the Quality Metric Health Outcomes™ Scoring Software will be used to derive SF-36 domain and component scores. After data quality-controls, the SF-36 software will recalibrate the item-level responses for calculation of the domain and component scores. These raw scores will be transformed into the domain scores (t-scores) using the 1-week recall period. This entails exporting the patient data in a CSV or tab-delimited file for import, generation of the SF-36 scores and reports, and export of the calculated scores in a CSV or tab-delimited file for integration into SDTM/ADAM datasets.	Missing data handling offered by SF-36 software will be used. “Maximum Data Recovery” will be selected for Missing Score Estimator in the software.
		SF-36 change from baseline for domain and component	Calculated as: observed SF-36 score – baseline SF-36 score	Missing if baseline or observed value is missing

Measure	Description	Variable	Derivation/Comment	Imputation Approach if with Missing Components
	The SF-36 acute version will be used, which has a 1 week recall period. Responder Definitions were determined in the user's manual (Maruish 2011).	scores		

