TSQM	
The Treatment Satisfaction Questionnaire for Medication (TSQM) is a self-administered 9-item measure to evaluate patient treatment satisfaction with medication in 3 domains:
 
 Effectiveness Item 1: prevention or treatment of 	TSQM Global Satisfaction	
Let “S” be the sum of all nonmissing items 7-9. TSQM Global Satisfaction is calculated as:
 $100 * (S - 3)/14$ 
If either Item 7 or 8 is missing:
 $100 * (S - 2)/10$ 
If Item 9 is missing:
 $100 * (S - 2)/8$	If more than 1 of the 3 items are missing, then missing

Measure	Description	Variable	Derivation/Comment	Imputation Approach if with Missing Components
	condition Item 2: symptom relief Item 3: time to start working Convenience Item 4: difficulty of use Item 5: difficulty in planning Item 6: convenience Global Satisfaction Item 7: confidence that medication is good Item 8: certain that good outweighs bad Item 9: overall satisfaction The recall period is the last 2-3 weeks or since the medication was last taken. Item formats include both a 1- to 7-point and a 1- to 5-point Likert scale. Higher scores indicate greater satisfaction (Bharmal et al. 2009).	TSQM Effectiveness	Let “S” be the sum of all nonmissing items 1-3. TSQM Effectiveness is calculated as: $100 * (S - 3)/18$ If one item is missing: $100 * (S - 2)/12$	If more than 1 of the 3 items are missing, then missing
		TSQM Convenience	Let “S” be the sum of all nonmissing items 4-5. TSQM Effectiveness is calculated as: $100 * (S - 3)/18$ If one item is missing: $100 * (S - 2)/12$	If more than 1 of the 3 items are missing, then missing.
QIDS-SR16	QIDS-SR16 is a self-administered, 16-item instrument intended to assess the existence and severity of symptoms of depression. A patient is asked to consider each item as it relates to the way they have felt over the last week. There is a 4-point scale for each item ranging from 0 (best) to 3 (worst). The domains assessed by the instrument include: (1) sleep disturbance (initial, middle, and late insomnia or hypersomnia); (2) sad mood;	QIDS-SR16 Total Score	The QIDS-SR16 total score is the sum of the domain scores below. The total score has a range of 0-27.	The total score will be missing if any domain score is missing.

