	DLQI (0,1)	CMH analysis with NRI	ITT - Patients with Baseline DLQI > 1	All scheduled visits in Induction Period; All scheduled visits in Induction and Maintenance Periods
	DLQI total score ≥ 5 -point reduction from baseline	CMH analysis with NRI	ITT - Patients with Baseline DLQI ≥ 5	All scheduled visits in Induction Period; All scheduled visits in Induction and Maintenance Periods
	DLQI total score and domain scores change from baseline	MMRM; ANCOVA with mBOCF	ITT	All scheduled visits in Induction Period; All scheduled visits in Induction and Maintenance Periods
SF-36	SF-36 change from baseline for PCS and MCS Component Scores and Domain Scores	ANCOVA with mBOCF	ITT	Last visit in Induction Period
		MMRM; ANCOVA with mBOCF	ITT	All scheduled visits in Induction and Maintenance Periods
	SF-36 PCS Responder Definition; SF-36 MCS Responder Definition; SF-36 Domain score Responder Definition;	CMH analysis with NRI	ITT	Last visit in Induction Period; All scheduled visits in Induction and Maintenance Periods
PatGA	PatGA(0)	CMH analysis with NRI	ITT - Patients with Baseline PatGA > 0	All scheduled visits in Induction Period; All scheduled visits in Induction and Maintenance Periods
	PatGA (0,1) and ≥ 2 -point improvement from baseline	CMH analysis with NRI	ITT - Patients with Baseline PatGA ≥ 2	All scheduled visits in Induction Period; All scheduled visits in Induction and Maintenance Periods
WPAI-PSO	Change from baseline in WPAI-PSO Scores (Absenteeism, Presenteeism, Work Productivity, Activity Impairment)	ANCOVA with mBOCF	ITT - Patients with Baseline Employment Status of Yes	Last visit in Induction Period
		MMRM; ANCOVA with mBOCF	ITT - Patients with Baseline Employment Status of Yes	All scheduled visits in Induction and Maintenance Periods

Description of Efficacy/Health Outcomes Analyses

Measure	Variable	Analysis Method (Section 6.1.2)	Population (Section 6.1.1)	Time Point and Period
TSQM	Mean Effectiveness, Convenience, and Global Satisfaction	ANCOVA with mBOCF	ITT	Last visit in Induction Period
		MMRM; ANCOVA with mBOCF	ITT	All scheduled visits in Induction and Maintenance Periods
EQ-5D-5L + Bolt On	Change from baseline of EQ-5D VAS and Index scores	MMRM; ANCOVA with mBOCF	ITT	All scheduled visits in Induction Period; All scheduled visits in Induction and Maintenance Periods
	EQ-5D Dimension Scores with no problems	CMH analysis with NRI	ITT	All scheduled visits in Induction Period; All scheduled visits in Induction and Maintenance Periods

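### TSQM Convenience is scored from two of its three items, and WPAI-PSO Activity Impairment is limited to patients employed at baseline

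*SAP*

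**What the plan says.** **TSQM Convenience (SAP Table AMAJ.6.5).** S is to "be the sum of all nonmissing items 4-5. TSQM Effectiveness is calculated as" 100 × (S − 3)/18, or 100 × (S − 2)/12 if one item is missing. The description column lists items 4 and 5 and then "Item 6: convenience" under the Convenience domain. The missing-data rule for the row is "If more than 1 of the 3 items are missing, then missing". Table AMAJ.6.6 takes the Convenience score into ANCOVA with mBOCF and into MMRM. TSQM does not appear among the protocol-defined endpoints in Table AMAJ.4.1.

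**WPAI-PSO Activity Impairment.** Table AMAJ.4.1 lists, among the other secondary endpoints, "Change from baseline for the WPAI PSO scores (Absenteeism, Presenteeism, Work Productivity Loss, and Activity Impairment", with no employment condition. In Table AMAJ.6.5 the item behind Activity Impairment is described as "degree of health affected productivity in regular unpaid activities". The missing-data rules for the work scores include "Also missing if Employment Status is No". The rule for Activity Impairment instead says "May still be present and nonmissing if patient is unemployed". Table AMAJ.6.6 puts all four scores together, and both of its WPAI-PSO lines use the population "ITT - Patients with Baseline Employment Status of Yes".

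**The concern.** The Convenience formula disagrees with the rest of its own entry. Table AMAJ.6.5 is the derivation specification. If it is programmed as printed, the score leaves its 0–100 scale, the item that asks about convenience itself contributes nothing, and a patient who skips an item may be placed on a different scale from one who answers everything.

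For WPAI-PSO, the restriction suits the three work scores, which do not exist for someone without a job. It has no evident purpose for a score about unpaid activities. Activity Impairment would be reported for a narrower population than the listed endpoint describes, with less precision if some patients are not employed at baseline, and the SAP gives no reason.

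**Working it through.** **TSQM: which items fit the constants.** For k items scored from 1 to m, a 0–100 transform subtracts the sum of the item minima and divides by the sum of the item ranges. The SAP says that both 7-point and 5-point formats occur but does not assign them to items.

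| Domain | Items tried | Offset / divisor | One item missing | Agrees with SAP? |
|---|---|---|---|---|
| Effectiveness | 1–3, all 7-point | 3 / 18 | 2 / 12 | Yes |
| Global Satisfaction | 7–9, as 5-, 5-, 7-point | 3 / 14 | 2 / 10 (item 7 or 8), 2 / 8 (item 9) | Yes |
| Convenience | 4–5, both 7-point | 2 / 12 | not applicable | No (SAP has 3 / 18) |
| Convenience | 4–6, all 7-point | 3 / 18 | 2 / 12 | Yes |

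The method reproduces the SAP's constants for the other two domains. Two items give a divisor of 8, 10 or 12, never 18. Of the eight 5/7-point combinations for items 4–6, only three 7-point items give 18.

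**TSQM: scores if programmed as printed (7-point items).**

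- All items answered, S from items 4–5: 100 × (2 − 3)/18 = −5.6 to 100 × (14 − 3)/18 = 61.1.
- All items answered, S from items 4–6: 100 × (3 − 3)/18 = 0 to 100 × (21 − 3)/18 = 100.
- Item 4 or 5 blank, as printed: 100 × (1 − 2)/12 = −8.3 to 100 × (7 − 2)/12 = 41.7.
- Item 6 blank, with the one-item-missing formula triggered by the three-item rule: 100 × (2 − 2)/12 = 0 to 100 × (14 − 2)/12 = 100.
- Every answered item equal to 4: complete data give 100 × (8 − 3)/18 = 27.8 as printed, against 100 × (12 − 3)/18 = 50. Item 6 blank gives 100 × (8 − 2)/12 = 50. Item 4 or 5 blank gives 100 × (4 − 2)/12 = 16.7.

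**TSQM: effect on a treatment difference (complete data).** If treatment shifts the items by d4, d5 and d6, the printed difference divided by the correct one is (d4 + d5)/(d4 + d5 + d6). Shifts of (1, 1, 0) give 1.00, (1, 1, 0.5) give 0.80, (1, 1, 1) give 0.67, (0.5, 0.5, 1) give 0.50 and (0, 0, 1) give 0.

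**WPAI-PSO: what the restriction sets aside.** The planned numbers are 888 mirikizumab, 444 secukinumab and 111 placebo, 1443 in all (SAP Section 5.2). The documents give no employment rate, so the fraction not employed, p, is an assumption, taken as equal across arms with the same outcome variance. The standard error is multiplied by 1/√(1 − p).

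| p | Set aside of 1443 | Kept: mirikizumab / secukinumab / placebo | SE factor |
|---|---|---|---|
| 0% | 0 | 888 / 444 / 111 | 1.000 |
| 10% | 144 | 799 / 400 / 100 | 1.054 |
| 20% | 289 | 710 / 355 / 89 | 1.118 |
| 40% | 577 | 533 / 266 / 67 | 1.291 |

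**The case against.** **TSQM.** The error is easy to recognise. The item list, the three-item rule and the constants all show that items 4–6 were meant, the wrong label looks copied from the Effectiveness row, and negative scores would alert a programmer. That is fair, and it makes this an erratum. It remains a derivation rule that is wrong as written and feeds planned analyses.

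The 0.67 ratio also applies to the raw difference only. The standard deviation shrinks as well when two items are summed instead of three. With equal shifts, equal variances and a common inter-item correlation r (all assumed), the standardised effect as printed is [2/√(2 + 2r)] / [3/√(3 + 6r)] of the correct one: 0.82 at r = 0, 0.94 at r = 0.5 and 0.97 at r = 0.7. With complete data, then, the larger harm is to the scale and its interpretation rather than to the test. The ratio can also exceed 1 if item 6 moves the other way. Finally, the item-6-blank case counts missing items over three while summing two. If both are read on two items, a blank item 6 changes nothing.

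**WPAI-PSO.** Tables AMAJ.6.5 and AMAJ.6.6 do not strictly contradict each other. The restriction is on baseline employment. A patient who loses a job during the study would have missing work scores but a usable Activity Impairment score, so the Table AMAJ.6.5 rule has a role inside the restricted population. The bullet in Table AMAJ.4.1 omits an employment limit for the work scores too, so its silence is weak evidence alone. Both points stand, and they remove any charge of outright error. They supply no reason to discard Activity Impairment data from patients not employed at baseline. Other endpoints in the same cell of Table AMAJ.4.1, such as those for scalp, nail and palmoplantar psoriasis, do state their baseline subset. Where the SAP knowingly departs from a listed endpoint, as for PatGA, it adds a footnote; here there is none.

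**Conclusion.** The concern holds on both entries, and both should be changed.

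- **TSQM Convenience** is wrong as written. The conclusion that three items were intended rests on the SAP's own item list, missing-data rule and constants. The numerical ranges rest on the inferred 7-point format.
- **Activity Impairment** is a valid comparison in a narrower population than the endpoint needs, with no justification. The size of the loss depends on an employment rate that the documents do not give, and at 0% not employed nothing is lost.

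The consequences are limited. WPAI-PSO is an other secondary endpoint, TSQM is outside Table AMAJ.4.1, and neither enters the graphical testing procedure.

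There is also a minor gap in completeness. Change from baseline in QIDS-SR16 total score, for patients with a baseline of 11 or more, is listed in Table AMAJ.4.1 but has no entry of its own in Table AMAJ.6.5 or AMAJ.6.6. Table AMAJ.4.1 gives its population and time points, and SAP Sections 6.1.2, 6.3.2 and 6.3.3 give default methods, so only the table entry is missing.

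**What to change.** 1. In Table AMAJ.6.5, define S for TSQM Convenience as the sum of nonmissing items 4–6 and relabel the formula as TSQM Convenience. The printed constants stay as they are.
2. In Table AMAJ.6.6, give Activity Impairment its own lines in all ITT patients, and keep the employed-at-baseline subset for Absenteeism, Presenteeism and Work Productivity Loss.
3. For completeness, add QIDS-SR16 total score change (observed minus baseline) to Table AMAJ.6.5, and an Induction Period row to Table AMAJ.6.6 for patients with a baseline of 11 or more, using the default methods. If Response and Remission are meant to replace it, a footnote like the one for PatGA is enough.

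The cost is two edited table entries, one added endpoint entry or footnote, and minor programming. No new data are needed.

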Induction and Maintenance Periods*	ITT; Induction and Maintenance PPS	placebo/250 miri; 300 secu; 250 miri Q4W/125 miri Q8W; 250 miri Q4W/250 miri Q8W; Total miri/miri (Note: Total miri represents the combined treatments of 250 miri Q4W/125 miri Q8W and 250 miri Q4W/250 miri Q8W.)	250 miri Q4W/125 miri Q8W vs 300 secu; 250 miri Q4W/250 miri Q8W vs 300 secu (For efficacy/healthoutcome measures, the comparisons will be only conducted from Week 20 to Week 52)
All Active Treatment Periods	All Active Treatments Safety	placebo/250 miri; 300 secu; 250 miri Q4W/125 miri Q8W; 250 miri Q4W/250 miri Q8W; all miri (Note: all miri represents the combined treatments of placebo/250 miri, 250 miri Q4W/125 miri Q8W and 250 miri Q4W/250 miri Q8W.)	250 miri Q4W/125 miri Q8W vs 300 secu; 250 miri Q4W/250 miri Q8W vs 300 secu

Treatment Groups and Comparisons for Each Study Period and Analysis Population

Study Period	Analysis Population	Treatment Groups	Inferential Comparisons
All Active Treatment + Follow-up Periods	All Active Treatment Safety	300 secu + FUP; all miri + FUP (Note: the header with “+ FUP” is used to emphasize that the observations from Follow-up Period are included.)	
All Periods	ITT	For study disposition only: placebo/250 miri; 300 secu; 250 miri Q4W/125 miri Q8W; 250 miri Q4W/250 miri Q8W; Total miri/miri	
	Induction Safety Population	For hepatic plot only: Ever on miri; Never on miri	

Abbreviations: FUP = follow-up; ITT = intent-to-treat; miri = mirikizumab; PPS = per protocol set; Q4W = every 4 weeks; Q8W = every 8 weeks; secu = secukinumab.

* For some analyses based on response status at certain weeks (Week 16 or 24), only maintenance period will be used, and the placebo/250 miri treatment group might not be displayed.

Note: for immunogenicity analysis, 300 secu treatment group will be excluded, thus the comparisons involving 300 secu will not be conducted; also the outputs for the “All Active Treatment Period” and “All Active Treatment + Follow-up Periods” will be combined.

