6.3.5. As Observed

Summary based on observed data at each postbaseline visit will be provided for some endpoints. Descriptive statistics will be reported without inferential comparisons. Only data from completers at the visit are relevant, and therefore the analysis does not need to deal with missing data. This estimand is based on the subset of patients who would complete treatment through the visit if assigned to it. Therefore, this estimand is conditional and targets the effect of treatment conditional on completion of treatment through the time point of interest. Because the estimand is defined for a subpopulation conditional on an intercurrent (postrandomization) event, it is not causal. The strategy used in this estimand is the one behind the so-called “observed cases” or “completers” analysis ubiquitous in the literature but is not one of the recommended strategies in the ICH E9(R1).

[figure not shown]

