Dimensions; EQ-5D-PSO = EuroQol 5 Dimensions – Psoriasis; MCS = Mental Component Score; NRS = Numeric Rating Scale; PCS = Physical Component Score; Q = question; QIDS-SR16 = 16-item Quick Inventory of Depressive Symptomatology; QoL = quality of life; SDTM = study data tabulation model; SF-36 = Short Form 36-item Health Survey; sPGA = Static Physician Global Assessment; VAS = visual analog scale.

Table AMAJ.6.6. Description of Efficacy/Health Outcomes Analyses

Measure	Variable	Analysis Method (Section 6.1.2)	Population (Section 6.1.1)	Time Point and Period
PASI	PASI 90 (Primary and Sensitivity)	CMH analysis with NRI	ITT; Induction PPS	Week 16 and all scheduled visits in Induction Period
			ITT; Induction and Maintenance PPS	Week 52 and all scheduled visits in Induction and Maintenance Periods
		Logistic regression analysis with NRI	ITT	Week 16 and all scheduled visits in Induction Period
		Tipping point analysis	ITT	Week 16
		Categorical MMRM	ITT	Week 16 and all scheduled visits in Induction Period
	PASI 75, PASI 100	CMH analysis with NRI	ITT	All scheduled visits in Induction Period; All scheduled visits in Induction and Maintenance Periods
	Time to first achieving PASI 100, PASI 90, or PASI 75 (i.e., 3 different analyses)	KM analysis (censoring described in Table AMAJ.6.5)	ITT	All scheduled visits in Induction Period
	Maintenance of PASI 90 response from Week 16 to Week 52	CMH analysis with NRI	ITT - Patients who are PASI 90 Responders at Week 16	Week 52 and all scheduled visits in Maintenance Period
	Maintenance of PASI 90 response from Week 24 to Week 52	CMH analysis with NRI	ITT - Patients who are PASI 90 Responders at Week 24	Week 52 and all scheduled visits in Maintenance Period
	Maintenance of PASI 100 response from Week 16 to Week 52	CMH analysis with NRI	ITT - Patients who are PASI 100 Responders at Week 16	Week 52 and all scheduled visits in Maintenance Period
Maintenance of PASI 100 response from Week 24 to Week 52	CMH analysis with NRI	ITT - Patients who are PASI 100 Responders at Week 24	Week 52 and all scheduled visits in Maintenance Period	
Stability of PASI 90 up to Week 52 from Week 16	CMH analysis with NRI	ITT	All scheduled visits in Maintenance Period	
		ITT - Patients who are PASI 90 Responders at Week 16	All scheduled visits in Maintenance Period	
Stability of PASI 100 up to Week 52 from Week 16	CMH analysis with NRI	ITT	All scheduled visits in Maintenance Period	

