		ITT - Patients who are PASI 100 Responders at Week 16	All scheduled visits in Maintenance Period	

Description of Efficacy/Health Outcomes Analyses

Measure	Variable	Analysis Method (Section 6.1.2)	Population (Section 6.1.1)	Time Point and Period
PASI	Cumulative time with PASI 90 response from Week 16 to Week 52; AUCs of PASI 90 response over time; Percentages of scheduled visits with PASI 90 response; Percentages of weeks with PASI 90 response	ANCOVA with factors: treatment, PASI baseline value, biologic therapy, body weight and geographic region	ITT - Patients who are PASI 90 Responders at Week 16	All scheduled visits in Maintenance Period
	Cumulative time with PASI 90 response from Week 0 to Week 52: AUCs of PASI 90 response over time; Percentages of scheduled visits with PASI 90 response; Percentages of weeks with PASI 90 response	ANCOVA with factors: treatment, PASI baseline value, biologic therapy, body weight and geographic region	ITT	All scheduled visits in Induction and Maintenance Periods
	PASI ≤ 5 ; PASI ≤ 3 ; PASI ≤ 2 ; PASI ≤ 1	CMH analysis with NRI	ITT	All scheduled visits in Induction Period; All scheduled visits in Induction and Maintenance Periods
	PASI change from baseline	MMRM; ANCOVA with mBOCF	ITT	All scheduled visits in Induction Period; All scheduled visits in Induction and Maintenance Periods
	Percentage improvement from baseline	MMRM; ANCOVA with mBOCF	ITT	All scheduled visits in Induction Period; All scheduled visits in Induction and Maintenance Periods
sPGA	sPGA (0,1) (Primary and Sensitivity)	CMH analysis with NRI	ITT; Induction PPS	Week 16 and all scheduled visits in Induction Period
			ITT; Induction and Maintenance PPS	Week 52 and all scheduled visits in Induction and Maintenance Periods
		Logistic regression analysis with NRI	ITT	Week 16 and all scheduled visits in Induction Period
		Categorical MMRM	ITT	Week 16 and all scheduled visits in Induction Period

Description of Efficacy/Health Outcomes Analyses

Measure	Variable	Analysis Method (Section 6.1.2)	Population (Section 6.1.1)	Time Point and Period
sPGA		Tipping point analysis	ITT	Week 16
	sPGA (0)	CMH analysis with NRI	ITT	All scheduled visits in Induction Period; All scheduled visits in Induction and Maintenance Periods
	Time to first achieving sPGA (0,1) or sPGA (0) (i.e., 2 different analyses)	KM product limit curve (censoring described in Table AMAJ.6.5)	ITT	All scheduled visits in Induction Period

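### Maintenance, responder-only stability and Week 16–52 cumulative PASI 90 time are tested between drugs in subsets chosen on post-randomisation response, so these supportive p-values can reflect selection

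*SAP*

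**What the plan says.** The PASI block of Table AMAJ.6.6 (SAP Section 6.11) restricts these analyses to on-treatment responders:

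- **Maintenance of PASI 90 and PASI 100 to Week 52, four rows.** CMH with nonresponder imputation, in subsets such as "ITT - Patients who are PASI 90 Responders at Week 16" and "ITT - Patients who are PASI 90 Responders at Week 24", with matching PASI 100 rows.
- **"Stability of PASI 90 up to Week 52 from Week 16"**, and the same for PASI 100. Each has one ITT row and one row in Week 16 responders.
- **"Cumulative time with PASI 90 response from Week 16 to Week 52; AUCs of PASI 90 response over time"**, with two percentage versions. ANCOVA, in Week 16 responders only.

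These are between-arm tests. Section 6.1.2 reports a CMH p-value for binary endpoints and Type III tests of LS means for ANCOVA. For the maintenance phase, the inferential column of Table AMAJ.6.2 lists each mirikizumab dose against secukinumab and no dose-against-dose comparison. Its footnote says "For some analyses based on response status at certain weeks (Week 16 or 24), only maintenance period will be used", but does not limit those analyses to description.

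The same table also has ITT analyses: PASI 90 and PASI 100 at scheduled visits through Week 52, the ITT stability rows, and "Cumulative time with PASI 90 response from Week 0 to Week 52: AUCs of PASI 90 response over time".

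Section 6.3.5, on the as-observed summary of completers, says "Descriptive statistics will be reported without inferential comparisons" and gives as a reason "Because the estimand is defined for a subpopulation conditional on an intercurrent (postrandomization) event, it is not causal".

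**The concern.** Who responds by Week 16 or 24 depends on the drug received. An arm with a lower Week 16 response rate contributes a more selected, easier-to-treat group to the maintenance denominator. An arm with a higher rate also contributes patients who only just responded. The covariates in Section 6.2 (prior biologic, weight, region), plus baseline PASI in the ANCOVA, cannot restore balance on unmeasured ease of response.

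A difference in maintenance percentage, with a p-value, would naturally be read as better durability than an active comparator. It could appear when the randomised Week 52 comparison shows nothing, and it can favour either drug. The responder-restricted rows cover nine variables (four maintenance, two stability, three cumulative-time). With two doses that makes 9 × 2 = 18 comparisons with secukinumab before by-visit repeats.

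Section 6.3.5 withholds inference from another subset defined by a post-randomisation event. The responder subsets share that feature, but the SAP sets no such limit on them.

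**Working it through.** **Inputs from SAP Section 5.2.** 444 patients in each mirikizumab dose group and in secukinumab; Week 16 PASI 90 of 70% on both drugs; Week 52 PASI 90 of 75% versus 65%; two-sided alpha 0.05; stated power 90% for Week 52 superiority.

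**Reproducing the stated power (ITT).**
- Null SE = √(2 × 0.70 × 0.30 / 444) = 0.03076.
- Alternative SE = √((0.75 × 0.25 + 0.65 × 0.35) / 444) = 0.03057.
- Power = Φ((0.10 − 1.96 × 0.03076) / 0.03057) = 90.3%, which agrees.

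The SAP gives no figure for the responder subsets.

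**Model for the subsets (assumed, not in the documents).** Week 16 and Week 52 response are thresholds on a bivariate normal variable with correlation ρ. Week 52 response is set to 70% in both arms, so the ITT Week 52 effect is zero. The maintenance proportion in an arm is P(response at both weeks) / P(response at Week 16). The comparison is an unstratified two-proportion test, standing in for CMH.

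**One case in full, ρ = 0.6, Week 16 rates 65% and 75%.**
- Responders: 444 × 0.65 = 289 and 444 × 0.75 = 333.
- Maintenance: 0.542/0.65 = 0.833 and 0.602/0.75 = 0.802, a gap of 3.1 points.
- Null SE = 0.0311; alternative SE = 0.0309.
- Rejection = Φ((0.0307 − 1.96 × 0.0311)/0.0309) + Φ((−0.0307 − 1.96 × 0.0311)/0.0309) ≈ 17%.

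**All cases, Week 52 response 70% in both arms.**

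| Week 16 rates | ρ | Maintenance proportions | Gap (points) | p<0.05 among responders | p<0.05, ITT Week 52 |
|---|---|---|---|---|---|
| 65% vs 75% | 0.4 | 0.784 vs 0.764 | 2.0 | 9% | 5% |
| 65% vs 75% | 0.6 | 0.833 vs 0.802 | 3.1 | 17% | 5% |
| 65% vs 75% | 0.8 | 0.894 vs 0.850 | 4.3 | 36% | 5% |
| 67% vs 73% | 0.4 | 0.780 vs 0.768 | 1.2 | 6.5% | 5% |
| 67% vs 73% | 0.6 | 0.827 vs 0.809 | 1.8 | 9% | 5% |
| 67% vs 73% | 0.8 | 0.886 vs 0.860 | 2.6 | 16% | 5% |
| 70% vs 70% | 0.6 in both | 0.818 vs 0.818 | 0 | 5% | 5% |

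The 10-point gap equals the non-inferiority margin in Section 6.6. It illustrates a difference that the design does not rule out in advance. It is not a forecast.

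**Can ITT stability take over as the durability test?** Table AMAJ.6.5 requires response from Week 16 onward, so a Week 16 nonresponder fails. As a proxy that ignores intermediate visits, take joint response at Weeks 16 and 52 with 444 per arm and Week 16 rates of 65% versus 75%. The proportions are 0.510 vs 0.573, 0.542 vs 0.602 and 0.581 vs 0.638 at ρ = 0.4, 0.6 and 0.8. Rejection is 47%, 44% and 41%. This is a valid randomised contrast, but it largely carries the induction difference and should not be labelled durability.

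**The case against.** The strongest case on the other side has four parts.

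- **The endpoints are supportive.** None is in Table AMAJ.4.1. Section 4 describes such endpoints as supportive, Section 6.5 limits alpha control to primary and major secondary endpoints, and the controlled Week 52 tests use ITT. This stands, and it caps the importance of the point.
- **The size depends on assumptions.** Under the SAP's equal Week 16 rates, with the same correlation in both arms, there is no inflation. The SAP also plans for a real Week 52 difference. This stands too. But the design tests Week 16 non-inferiority, so exact equality cannot be presumed.
- **Maintenance percentages describe something real.** In the illustration, response in one arm falls from 75% to 70% while the other rises from 65% to 70%. The maintenance percentages are legitimate descriptions of each arm. What fails is reading their difference, with a p-value, as a randomised drug effect.
- **ITT counterparts exist.** A reader might infer that durability and cumulative time are analysed only in responders. The documents do not support that: stability has ITT rows, and cumulative time from Week 0 to 52 is listed as ITT. What remains is that neither maintenance nor the Week 16–52 cumulative-time variable has an ITT row of its own.

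A reader might also infer that the SAP itself calls the responder subsets non-causal. It does not. The sentence in Section 6.3.5 concerns completers and applies here only by analogy. The analogy is imperfect, because the maintenance rows count later missing data as nonresponse.

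**Conclusion.** The point holds at modest weight. The responder-restricted rows attach between-drug p-values to groups that randomisation does not balance. With no Week 52 difference, the rejection rate rises from 5% to about 9–36% for an assumed 65% versus 75% Week 16 gap, and to about 6.5–16% for 67% versus 73%. It stays at 5% under the planned equal rates with equal correlation. These figures rest on the assumed latent-normal model, correlations of 0.4–0.8, the assumed Week 16 gaps and an unstratified test. They were computed for the maintenance proportion; the responder-only stability rows and the cumulative-time ANCOVA share the selection but were not simulated.

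It would go too far to infer that a primary or major secondary conclusion is at risk. Those tests use ITT, or subsets defined at baseline.

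**What to change.** 1. In Table AMAJ.6.6, report every row restricted to Week 16 or Week 24 responders by arm, with n, percentage or mean, and confidence interval. Omit between-arm p-values and state that these are not randomised comparisons. Repeat this in the footnote to Table AMAJ.6.2.
2. Add an ITT row for cumulative PASI 90 time from Week 16 to 52.
3. Base between-arm inference on the ITT analyses: PASI 90 and PASI 100 by visit and at Week 52, cumulative time, and stability. Describe ITT stability as response achieved by Week 16 and kept, not as durability alone.
4. Reconcile the Week 0–52 cumulative-time population. Table AMAJ.6.5 describes its AUC as being among PASI 90 responders from Week 0, whereas Table AMAJ.6.6 gives ITT.

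The cost is SAP wording, a few supportive p-values lost and one analysis row added. No new data are needed.
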